2.1. Study Rationale

This Phase 3 study will evaluate the efficacy and safety of once-weekly administration of LY3209590 on glycemic control compared with daily administration of insulin degludec in adult participants with T1D treated with MDI therapy. This study will inform the clinical development of LY3209590.

2.2. Background

Current state of diabetes care

There have been many advances in the treatment of T1D; however, reaching and maintaining glycemic goals while managing the risk of hypoglycemia remain challenging.

Potential for improved treatment regimens

Once-weekly basal insulins with a lower peak-to-trough profile during the week and a nearly flat insulin profile could reduce within-day glucose variability and result in more consistent and predictable glycemic control.

LY3209590

LY3209590 is a novel insulin receptor agonist that is in development as a once-weekly basal insulin for the treatment of patients with T1D and T2D. LY3209590 was designed as a divalent (dimer) insulin receptor agonist consisting of a single-chain insulin analog (comprised of an insulin B-chain analog, a short peptide linker, and an insulin A-chain analog) fused to a second peptide linker that is fused to an unmodified human IgG2 Fc domain.

A detailed description of the chemistry, pharmacology, non-clinical and clinical efficacy, and safety of LY3209590 is provided in the Investigator's Brochure.

Summary of clinical results

Phase 1 and Phase 2 studies have been completed to assess the PK/PD, safety, and efficacy of LY3209590. The results thus far support continued development of LY3209590 as a treatment for diabetes mellitus.

Phase 1 study results

LY3209590 pharmacokinetics show a low peak-to-trough ratio and extended mean half-life of 17 days that supports once-weekly dosing. Single-ascending doses of LY3209590 lowered fasting glucose in a dose- and concentration-dependent manner, with a prolonged time-action profile.

Phase 2 study BDCM results comparing LY3209590 to insulin degludec in patients with T2D

Study BDCM was a randomized, open-label, Phase 2 study to evaluate the safety and efficacy of LY3209590 in participants with T2D previously treated with basal insulin.

LY3209590 was noninferior to degludec for glycemic control as measured by change in HbA1c from baseline to Week 32 with significant improvement in HbA1c in all treatment groups with a lower risk of hypoglycemia with LY3209590.

The overall adverse event profile from Study BDCM showed no increased safety risk with LY3209590 compared with degludec treatment.

Phase 2 study BDCP comparing LY3209590 to insulin degludec in patients with T1D

Study BDCP was a randomized, open-label, Phase 2 study to evaluate the safety and efficacy of LY3209590 in patients with T1D treated with MDI therapy.

LY3209590 was noninferior to degludec as measured by change in HbA1c from baseline to Week 26, although participants treated with LY3209590 had higher fasting glucose at study endpoint. Over 26 weeks of study treatment, the rate of Level 2 hypoglycemia and nocturnal hypoglycemia as well as time below range from CGM were not significantly different between groups.

The overall adverse event profile from Study BDCP in patients with T1D showed no increased safety risk with LY3209590 compared with degludec treatment.

2.3. Benefit/Risk Assessment

Detailed information about the known and expected benefits and risks and reasonably expected adverse events of LY3209590 may be found in the Investigator's Brochure, and that of insulin degludec may be found in the local product package insert.

2.3.1. Risk Assessment

Potential risks for this study

The potential risks associated with LY3209590 include

- hypoglycemia
- hyperglycemia
- hypersensitivity reaction
- injection site reactions, for example, injection site rash, erythema, pruritus, or lipohypertrophy
- immunogenicity, and
- cardiovascular risks.

It is expected that the known risks would be similar to other insulins.

Safety data available to date suggest that there is no increased risk to participants' safety with LY3209590 treatment compared to insulin degludec.

Management of risks

Sections 5.1, 5.2, 7, and 8.3 address known potential risks associated with LY3209590.

Protocol risk management measures

Participant education for hypoglycemia

After signing informed consent, all participants will be educated about signs and symptoms of hypoglycemia, how to treat hypoglycemia, and how to collect appropriate information for hypoglycemia events. Hypoglycemia may be identified by spontaneous reporting of symptoms from participants, whether confirmed or unconfirmed by simultaneous glucose values, or by blood glucose samples collected between study visits.

Monitoring of participant CGM and blood glucose levels

All participants will use the study-provided, unblinded CGM system to facilitate diabetes and hypoglycemia management and for data collection throughout the study. A web interface will be available for site personnel to download and review CGM data.

Each participant will have a study-provided glucometer that will wirelessly transfer participant SMBG to their study-provided e-diary. Participants should check glucose values with the glucometer when hypoglycemia is experienced or suspected.

A web interface and reporting system will be available for use by study personnel to view participant e-diary entries, including SMBG, insulin doses, and hypoglycemia information throughout the study. Automated alerts will be transmitted to the investigator any time the participant reports a potential severe episode of hypoglycemia, defined as requiring assistance due to neurological impairment, in the e-diary.

Dose modification

The basal insulin dosing algorithm used in the study requires consideration and adjustment of insulin dosing by the investigator based on participant FBG, CGM data, and hypoglycemia events (see Section 6.5).

All participants will be treated with basal-bolus MDI therapy, which will be titrated to glycemic targets and as clinically indicated for hyperglycemia.

2.3.2. Benefit Assessment

Participants may benefit during the study by frequent engagement and support from health care providers for diabetes management and safety assessments with the potential to improve glycemic control.

2.3.3. Overall Benefit Risk Conclusion

Considering the clinical data to date and measures taken to minimize risk for the participants in this study, the potential risks identified in association with LY3209590 are justified by the anticipated benefits that may be afforded to participants with T1D.

3. Objectives, Endpoints, and Estimands

Objectives	Endpoints
Primary	
To demonstrate that LY3209590 is noninferior to insulin degludec for the treatment of T1D in adults	
 Change in HbA1c from baseline to Week 26
Key Secondary (multiplicity adjusted)	
To demonstrate superiority of LY3209590 to insulin degludec	
 Change in HbA1c from baseline to Week 26 Time in glucose range between 70 and 180 mg/dL (3.9 and 10.0 mmol/L) inclusive, measured by CGM 4 weeks prior to Week 26 Event rate of participant-reported clinically significant nocturnal hypoglycemia (<54 mg/dL [3.0 mmol/L] or severe) during treatment phase up to Week 52
Other Secondary	
To investigate the effect of LY3209590 compared with insulin degludec in additional parameters of glycemic control	
 Change in HbA1c from baseline to Week 52 Change from baseline to Weeks 26 and 52 in fasting glucose as measured by SMBG Glucose variability, measured by CGM 4 weeks prior to Weeks 26 and 52 Time in glucose range between 70 and 180 mg/dL (3.9 and 10.0 mmol/L) inclusive, measured by CGM 4 weeks prior to Week 52 Insulin dose at Weeks 26 and 52 
 basal bolus total, and basal/total insulin dose ratio

To compare the safety of LY3209590 to insulin degludec	
 • Rate of composite of Level 2 and 3 hypoglycemia events during treatment period • Body weight change from baseline to Weeks 26 and 52 • Time in hypoglycemia range with glucose <54 mg/dL (3.0 mmol/L), measured by CGM 4 weeks prior to Weeks 26 and 52 • Time in hyperglycemia range defined as glucose >180 mg/dL (10.0 mmol/L), measured by CGM 4 weeks prior to Weeks 26 and 52
To compare treatment satisfaction and health-related quality of life between LY3209590 and degludec as assessed by patient-reported outcome questionnaires	
 • DTSQ change from baseline to Weeks 26 and 52 • Change in SF-36 v2 acute form domain scores from baseline to Weeks 26 and 52
Tertiary	
To investigate the effect of LY3209590 compared with insulin degludec on other measures of efficacy, safety, and patient-reported outcomes	
Efficacy
 
 • Percentage of participants achieving HbA1c < 7% at Weeks 26 and 52 • Percentage of participants achieving HbA1c \leq 6.5% at Weeks 26 and 52 • Change from baseline to Weeks 26 and 52 in fasting serum glucose as measured by central laboratory
	
Safety
 
 • Rate and incidence of Level 2 hypoglycemia events during treatment period • Rate and incidence of Level 3 hypoglycemia events during treatment period • Incidence of positive treatment-emergent antibody of LY3209590

	
Patient-reported outcomes
 
 Frequency of responses to “Basal Insulin Experience: Likelihood of incorporating into routine” at Weeks 26 and 52 Frequency of responses to “Basal Insulin Experience: Preference” at Weeks 26 and 52 Change in EQ-5D-5L from baseline to Weeks 26 and 52
To characterize the PK/PD of LY3209590	
 LY3209590 PK and concentration response relationships to key safety and efficacy measures.

Abbreviations: CGM = continuous glucose monitoring; DTSQ = Diabetes Treatment Satisfaction Questionnaire; HbA1c = hemoglobin A1c; PK/PD = pharmacokinetics/pharmacodynamics; SF-36 = Short Form-36 Version 2 Health Survey Acute Form; SMBG = self-monitoring of blood glucose; T1D = Type 1 diabetes.

Primary estimand

United States registration

The primary clinical question of interest is

What is the treatment difference between LY3209590 and insulin degludec in HbA1c change from baseline after 26 weeks of treatment, in study eligible participants with T1D treated with MDI therapy, regardless of treatment discontinuation for any reason and regardless of initiation of rescue medication?

Treatment regimen estimand attributes

This table describes the treatment regimen estimand attributes.

Treatment Regimen Estimand Attributes	Description
Population	Targeted study population (see table in Section 9.2).
Endpoint	HbA1c change from baseline to Week 26.
Remaining intercurrent events	None. The 2 intercurrent events, treatment discontinuation for any reason and initiation of rescue medication, are both addressed by the treatment condition of interest attribute.
Treatment condition	The randomized treatment regardless of treatment discontinuation and use of rescue medications.

Population-level summary	Difference in mean changes between treatment conditions.
--------------------------	--

Rationale for the treatment regimen estimand

The treatment regimen estimand estimates how participants with T1D are treated in clinical practice and considers both efficacy and safety.

Registration for countries outside the United States

The primary clinical question of interest is

What is the treatment difference between LY3209590 and insulin degludec in HbA1c change from baseline after 26 weeks of treatment, in study eligible participants with T1D treated with MDI therapy and adhere to the randomized treatment without an intercurrent event during the study treatment period?

Efficacy estimand attributes

This table describes the efficacy estimand attributes.

Efficacy Regimen Estimand Attribute	Description
Population	Targeted study population. (see table in Section 9.2).
Endpoint	HbA1c change from baseline to Week 26.
Remaining intercurrent events	None. The 2 intercurrent events, treatment discontinuation for any reason and initiation of rescue medication, are both addressed by the hypothetical strategy, for example, the potential outcome for those participants if the intercurrent events have not occurred will be estimated.
Treatment condition	The randomized treatment.
Population-level summary	Difference in mean changes between treatment conditions.

Rationale for the efficacy estimand

The efficacy estimand supports the interpretation of the treatment effect as participants adhere to study treatment and free from the confounding effect of rescue medications.

Secondary estimands for multiplicity-adjusted objectives

The superiority test in change from baseline to Week 26 (Visit 22) in HbA1c will also be based on the primary estimand described above.

The time in glucose range between 70 and 180 mg/dL (3.9 and 10.0 mmol/L), inclusive, measured by CGM in the 4 weeks prior to Visit 22 (Week 26) will use treatment regimen estimated for US registration and efficacy estimand for other countries.

The participant-reported clinically significant nocturnal hypoglycemia (<54 mg/dL [3.0 mmol/L] or severe) is one of the safety measures for the study. The event rate will be based on all available data during the specific analysis period. Relative rate between randomized treatment groups will be used for treatment comparison.

4. Study Design

4.1. Overall Design

This is a Phase 3, open-label, 2-arm, parallel-design, randomized control study to investigate if LY3209590 is noninferior to insulin degludec in adult participants with T1D who are treated with basal-bolus insulin MDI therapy.

The study consists of a 1-week screening period, a 2-week lead-in period, a 52-week treatment period, and a 5-week safety follow-up period.

Visit 1: Screening

Interested participants will sign the appropriate informed consent document(s) prior to initiating any procedures.

The investigator will review medical history, symptoms, risk factors, and other inclusion and exclusion criteria prior to any diagnostic procedures. If the participant is eligible after this review, then the site will perform the diagnostic procedures to confirm eligibility.

Visit 2: Lead-In

Participants will receive their glucometer, electronic study diary, and unblinded CGM system.

Participants will receive training on

- diabetes self-monitoring and management
- unblinded CGM system
- glucometer and e-diary, and
- study requirements.

Starting with Visit 2, participants will use the study-supplied glucometer, e-diary, and unblinded CGM system for diabetes management and data collection throughout the study.

Participants will continue with their current basal-bolus insulin therapy until randomization.

Treatment period

Visit 3 (Week 0): Randomization

This is the general flow for Visit 3

- study personnel confirm enrollment criteria
- participants are randomly assigned to an intervention group (LY3209590 or insulin degludec)
- study personnel complete baseline procedures and sample collection
- study personnel will provide study insulin dosing training
 - For participants randomized to LY3209590, the first dose of LY3209590 will be administered at the site by study personnel or by the participant under observation of study personnel. Insulin dose information will be entered in the e-diary.
 - For participants randomized to insulin degludec, the first dose of degludec can be administered at the site or after the visit, depending upon the usual time of basal insulin dosing.

- study personnel complete all visit procedures.

Participants assigned to insulin degludec will be treated with daily dosing of degludec after Visit 3.

Participants will be treated with insulin lispro as prandial insulin throughout the treatment period as described in Section [6.5.3](#).

Visit 4 (Week 1)

Participants complete all visit procedures described in the SoA.

Study personnel will provide dosing training and observe participants administer their second dose of LY3209590.

Visit 5 through Visit 29 (Week 2 through Week 52)

Study personnel and participants complete all visit procedures described in the SoA.

The participant's BG and CGM data will be used to titrate basal and prandial insulin dosing as described in Section [6.5](#).

The investigator or study staff will review participant e-diary compliance for

- SMBG
- hypoglycemia events, including related signs and symptoms, and
- study intervention compliance, including insulin dose data.

Last study treatment visit: either V29 (Week 52) or ED visit

Participants complete all visit procedures described in the SoA.

Participants will return any unused study intervention to the investigative site.

The investigator will determine the participant's basal and prandial insulin treatment during the safety follow-up period as described in Section [6.6.1](#).

Safety follow-up visits 801 and 802

Study personnel and participants complete all visit procedures described in the SoA.

The investigator will follow up on the participant's transition to non-study basal and prandial insulin treatment.

Participants will return study devices at the final study visit.

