Physical examination	X																	Additional physical examinations may be completed as necessary at investigator discretion.	

Study I8H-MC-BDCY Table 1	Screening and Lead-In		Treatment															Comments	
			1	2	3	4	5	6	7	8	9	10	11	12	13	14	15		
Visit Number			1	2	3	4	5	6	7	8	9	10	11	12	13	14	15	16	
Weeks from Randomization	-3	-2	0	1	2	3	4	5	6	7	8	9	10	11	12	13	14		
Visit Interval Tolerance (days)			±3	—	±3	±3	±3	±3	±3	±3	±3	±3	±3	±3	±3	±3	±3		
Visit Detail					F				F								F	T	T = telehealth visit F = fasting visit
12-lead ECG (local)	X																		Collect prior to collection of blood samples. Participants should be supine for approximately 5 to 10 min before ECG collections and remain supine but awake during the ECG collection. ECGs may be repeated at the investigator's discretion at any visit.
Unblinded continuous glucose monitoring																			
Dispense CGM system		X																	Dispense CGM supplies as needed after Visit 2.
Download and review CGM data in study vendor portal			X	X	X	X	X	X	X	X	X	X	X	X	X	X			
Discuss CGM and hypoglycemia data			X	X	X	X	X	X	X	X	X	X	X	X	X	X	X		
Participant education																			
Diabetes counseling, training, and education		X	X																Includes glucose monitoring and hypoglycemia (see Sections 5.3, 8.1.1, and 8.3.6). After Visit 3, conduct as needed.
e-diary, glucometer, and CGM training		X	X																After Visit 3, conduct as needed.

Study I8H-MC-BDCY Table 1	Screening and Lead-In		Treatment														Comments	
			1	2	3	4	5	6	7	8	9	10	11	12	13	14	15	16
Visit Number																		
Weeks from Randomization	-3	-2	0	1	2	3	4	5	6	7	8	9	10	11	12	13	14	
Visit Interval Tolerance (days)			±3	—	±3	±3	±3	±3	±3	±3	±3	±3	±3	±3	±3	±3	±3	
Visit Detail			F				F									F	T	T = telehealth visit F = fasting visit
Electronic participant diary and glucometer																		
Dispense e-diary and glucometer		X																Dispense glucometer supplies as needed after Visit 2.
Diary compliance check			X	X	X	X	X	X	X	X	X	X	X	X	X	X	X	Review entries of BG, hypoglycemia events, and insulin dose. If participant is not compliant, study personnel will re-educate the participant on study requirements for continued study participation. See Sections 6.4 and 8.1.1 for additional details.
Electronic patient-reported outcomes																		
Diabetes Treatment Satisfaction Questionnaire – Status (DTSQs)			X															
SF-36 v2 acute form			X															
EQ-5D-5L			X															

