4.2. Scientific Rationale for Study Design

Primary endpoint

The primary efficacy measurement is HbA1c, a widely used measure of glycemic control that reflects a cumulative history of glucose levels in the preceding 2 to 3 months.

Overall design

Blinding

This is an open-label study. Investigators, participants, and study-site personnel will be unblinded to the assigned treatment. To eliminate potential biases, designated members of the Lilly study team will remain blinded throughout the study (see Section 6.3). Only a minimum number of Lilly personnel will see the randomization table and treatment assignments before the study is complete.

Study duration

The treatment duration is a reasonable timeframe to observe the effects of LY3209590 compared to insulin degludec.

The follow-up visits after the last dose is designed to capture any additional safety signals and to monitor the transition from study treatment to non-study insulins.

Comparator

Insulin degludec was chosen as the comparator because it is widely accepted as the best-in-class basal insulin. It has the longest half-life among other marketed basal insulins.

Collection of race and ethnicity data

In this study, collection of demographic information includes ethnicity (where permissible) and race. The scientific rationale is based on the need to assess variable response in safety and/or efficacy based on race or ethnicity. This question can be answered only if all the relevant data are collected.

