6.3. Measures to Minimize Bias: Randomization and Blinding

Randomization and stratification

All participants will be centrally assigned to randomized study intervention using an IWRS. Before the study is initiated, the log-in information and directions for the IWRS will be provided to each site.

Participants will be randomly assigned in a 1:1 ratio to LY3209590:insulin degludec.

Participants will be stratified based on

- country
- HbA1c stratum (<8% and ≥8%) at screening Visit 1
- CGM use prior to study entry (yes/no), and
- carbohydrate counting for prandial insulin dosing (yes/no).

Blinding

This is an open-label study. Investigators and participants will be unblinded to the assigned treatment groups.

The Lilly study team members who are closely involved in data interpretation and analysis planning will remain blinded throughout the course of the study. Only a minimum number of Lilly personnel will see the randomization table and treatment assignments before the study is complete.

The investigator should make every effort to preserve the blinding when contacting the Lilly study team members, including the Lilly clinical research physician or scientist.

Unblinded reviews

External committees reviewing unblinded data during the study are described in Section [10.1.5](#)

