8.1.2. Patient-Reported Outcomes

The self-administered questionnaires will be translated into the native language of the region and administered at the site during the designated visits in the SoA (Section 1.3).

Order of administering the questionnaires during the visit

The questionnaires should be completed before the participant has discussed their medical condition or progress in the study with the investigator or study personnel, if the participant is not adversely affected by their fasting condition.

The order of administration of these questionnaires, where applicable, is

- Diabetes Treatment Satisfaction Questionnaire - Status
- Diabetes Treatment Satisfaction Questionnaire - Change
- SF-36v2 acute form
- EQ-5D-5L
- Basal Insulin Experience: Preference, and
- Basal Insulin Experience: Likelihood of incorporating into routine.

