Laboratory values elevated or low, vital signs, and body weight categorical measures	
Starts from the screening visit and ends prior to or on the first dose date of the study treatment.
 
All available measurements at scheduled and unscheduled visits will be included. The baseline for weight will be the last non-missing value during the baseline period.
	
Starts after the day of first dose of study treatment and ends at the last visit in the study, including both the treatment period and follow-up period.
 
All available measurements at scheduled and unscheduled visits in the specified analysis period will be included.

Anti-LY3209590 antibodies	Refer to PSAP	Refer to PSAP
Patient-reported outcomes	Baseline will be the data collected at Visit 3.	
 • All scheduled visits after Week 0 (Visit 3) • Last collection after Week 0 (Visit 3)

Abbreviations: AE = adverse event; CGM = continuous glucose monitoring; CRF = case report form; EAS1 = Efficacy Analysis Set 1; EAS2 = Efficacy Analysis Set 2; HbA1c = hemoglobin A1c; MMRM = mixed model of repeated measures; PSAP = Program Safety Analysis Plan; SMBG = self-monitored blood glucose; TEAE = treatment-emergent adverse event.

All analyses will be implemented using SAS Enterprise Guide Version 7.1 or above.

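### The Visit 3 flow lets the baseline SF-36 v2 and EQ-5D-5L be answered after the arm is known; these questionnaires should be required before randomisation

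*Protocol*

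**What the plan says.** Protocol 4.1 introduces the Visit 3 steps with "This is the general flow for Visit 3" and lists them in this order:

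1. eligibility is confirmed;
2. "participants are randomly assigned to an intervention group (LY3209590 or insulin degludec");
3. "study personnel complete baseline procedures and sample collection";
4. dosing training is given, with the first LY3209590 dose taken at the site.

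Nothing conceals the result of step 2. Protocol 4.2 states: "Investigators, participants, and study-site personnel will be unblinded to the assigned treatment".

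The Schedule of Activities places the only baseline DTSQs, SF-36 v2 and EQ-5D-5L at Visit 3, with no comment on timing within the visit. SAP 4.1 defines the baseline for patient-reported outcomes in one line: "Baseline will be the data collected at Visit 3". Protocol 8.1.2 adds a rule for all visits: "The questionnaires should be completed before the participant has discussed their medical condition or progress in the study with the investigator or study personnel". That rule is waived for a participant who is adversely affected by fasting.

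**The concern.** A baseline covariate should be out of reach of the allocation. If a site follows the listed order, the participant may learn at step 2 whether the next year brings a weekly or a daily basal injection, and then rate their health at step 3. Any reaction to that news is recorded as baseline.

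SF-36 v2 domain change is an Other Secondary endpoint and EQ-5D-5L change is tertiary. A baseline that the arm can move no longer serves as a neutral adjustment and becomes a source of bias, which a larger sample does not reduce. The planned between-arm test of the baseline DTSQs could not tell a chance imbalance from a reaction to the arm.

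**Working it through.** The plan gives no power or precision figure for any patient-reported outcome, so there is nothing of its own to reproduce. The check is of the wording first, then of the form and possible size of the bias.

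**Does any passage place the questionnaires before randomisation?**

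| Place | What it fixes | What it leaves open |
|---|---|---|
| Protocol 4.1, Visit 3 | Allocation listed before baseline procedures | Described as general, so the order can vary by site |
| Schedule of Activities, Visit 3 | Eligibility confirmed before randomisation; biomarker samples before dosing | No timing for the questionnaires |
| Protocol 8.1.2 | Questionnaires before discussion of condition or progress | Advisory (should), fasting exception, silent on allocation; Visit 3 appears to be a fasting visit |
| SAP 4.1 | Baseline is the Visit 3 record | No limit relative to randomisation or first dose |
| SAP 4.4.2.3.1 | DTSQs before study treatment starts | The interval between randomisation and first dose; does not cover SF-36 v2 or EQ-5D-5L |

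None of them does.

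**Which analyses use the Visit 3 score?**

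- SF-36 v2 (SAP 4.4.2.3.2) and EQ-5D-5L index and VAS (SAP 4.4.2.3.3): the baseline is part of the change score and a covariate in the MMRM and the ANCOVA. Exposed.
- DTSQc (SAP 4.4.2.3.1): a Wilcoxon rank-sum test with no baseline term. Not exposed.
- DTSQs: scheduled only at baseline, so only its baseline summary and test are exposed.

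**Form of the bias.** Let d be the shift in mean baseline, LY3209590 minus degludec, caused by knowing the arm. Let b be the slope of follow-up score on baseline. Suppose the follow-up scores are unaffected by when the baseline was taken.

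- Unadjusted change score: the difference moves by -d.
- Change score with baseline as covariate: the slope of change on baseline is b - 1, so the adjusted difference moves by -d - (b - 1)*d = -b*d.

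The planned models therefore subtract the fraction b of the shift. Descriptive mean changes carry all of it.

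**Possible size for SF-36 v2.** The documents supply the scale (T-score, SD 10) and 284 Week 26 completers per arm. The assumptions are d of 0.5 to 2 points, b of 0.4 to 0.8, an SD of 10 in the trial at both times, and no gain from the other covariates. Then SE = 10*sqrt(1 - b^2)*sqrt(2/284). For b = 0.6 this is 10*0.8*0.0839 = 0.671. The last column is the two-sided rejection rate at nominal 5% when the true difference is zero.

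| d | b | bias -b*d | SE | rejection rate |
|---|---|---|---|---|
| 0.5 | 0.4 | -0.2 | 0.769 | 5.8% |
| 0.5 | 0.6 | -0.3 | 0.671 | 7.3% |
| 0.5 | 0.8 | -0.4 | 0.504 | 12.5% |
| 1 | 0.4 | -0.4 | 0.769 | 8.2% |
| 1 | 0.6 | -0.6 | 0.671 | 14.5% |
| 1 | 0.8 | -0.8 | 0.504 | 35.5% |
| 2 | 0.4 | -0.8 | 0.769 | 18.0% |
| 2 | 0.6 | -1.2 | 0.671 | 43.2% |
| 2 | 0.8 | -1.6 | 0.504 | 88.8% |

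Here d is an average over all participants. If half of the baselines in each arm were completed after allocation and the reaction among those was 1 point, then d = 0.5*1 = 0.5 and the first three rows apply. With every questionnaire completed before randomisation, d is zero in expectation.

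**The case against.** The best defence is that Protocol 4.1 gives only a general flow, while 8.1.2 is the specific rule. At Visit 3 staff review eligibility, adverse events and CGM and hypoglycaemia data, and eligibility must be settled before randomisation. A site that gives the questionnaires ahead of those conversations will normally give them ahead of allocation too. This is a fair reading, and many sites may work that way. But the rule is aimed at a different influence, is advisory, and falls away for a participant troubled by fasting. It also sits awkwardly with the order in 4.1. The two passages need reconciling.

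A second argument is that a same-visit shift is unlikely to be large. All SF-36 domains except Physical Functioning ask about the past week, and the DTSQs about the past few weeks. This stands as a reason to expect a small d. The documents do not show that it is zero.

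Third, the stakes are limited. SAP 2.1 makes no multiplicity adjustment for these endpoints, and the Week 26 and 52 answers are given open-label whatever happens at baseline. That also stands, and it limits the weight of the point. It is no reason to leave an avoidable bias in the baseline.

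**Conclusion.** The point holds for SF-36 v2 and EQ-5D-5L: as written, their baselines can be collected after the arm is known, and the planned analyses would carry -b*d of any resulting shift. The gap in the wording is certain. The size is not, because b and d are assumptions and the table shows only what they would imply.

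A reader might infer more than the documents support:

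- **That the primary endpoint is at risk.** HbA1c is a central laboratory value reflecting the preceding 2 to 3 months, so learning the arm within a visit cannot plausibly change it.
- **That the treatment-satisfaction comparison is biased.** The planned post-baseline comparison uses DTSQc and no baseline term.
- **That the whole reaction is removed from the treatment effect.** In the adjusted models only the fraction b is.
- **That the order flatters the new insulin.** A favourable reaction to a weekly injection, or disappointment at a daily one, makes d positive and biases against LY3209590. The opposite reaction would reverse the sign.
- **That baselines were in fact contaminated.** The documents do not show how sites ordered the visit.

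**What to change.** **Protocol.** In 4.1, in the Schedule of Activities rows for the three instruments, and in 8.1.2, state that the Visit 3 DTSQs, SF-36 v2 and EQ-5D-5L are completed before IWRS randomisation. Leave sample timing as it is. Protocol 8.8 requires the Visit 3 PK sample for LY3209590 after dosing, so moving all sample collection ahead of randomisation would create a new contradiction.

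**SAP.** In 4.1, define the baseline for patient-reported outcomes as the Visit 3 record completed before randomisation.

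**Participants already randomised.** Where time stamps exist, compare ePRO completion with IWRS randomisation times and report by arm how many baselines came later. Repeat the SF-36 v2 and EQ-5D-5L analyses without those baselines, as a sensitivity analysis. The documents describe electronic capture and central randomisation but do not confirm that comparable time stamps are kept.

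**Cost.** There are no new visits or procedures. The protocol wording is one amendment line, though Protocol 10.1.1 requires ethics approval of amendments. The SAP needs one sentence and a small extra analysis. SAP version 3 was approved just ahead of the final lock stage of the trial, so for this study the time-stamp check is probably the part with most practical value.
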